6.26 Quality of Life (QoL)

Patients receiving FWGE may experience a positive or negative affect on QoL relative to those who receive placebo.

The measures used in this study to assess QoL are the self-administered Functional Assessment of Cancer Therapy questionnaire for ovarian cancer (FACT-O) a 39-question assessment. Patients will be asked to complete these questionnaires at the following time points during their participation in the study:

- At the time of enrollment
- ii. Weekly
- iii. Prior to surgery

Construct and content

The Functional Assessment of Cancer Therapy scale developed for ovarian cancer (FACT-O) is a tool that provides a general QoL score. It consists of 3 subscales: physical well-being (7 items), social/family well-being (7 items), emotional well-being (6 items), functional well-being (7 items), and the Ovarian Cancer subscale (12 items). This questionnaire has been found to be valid and reliable [21].

Descriptive statistics from the baseline QoL data will be calculated. These will include descriptions of the distribution of QoL scores (mean, standard deviation, median, etc.). For all patients the baseline scores will be calculated using the questionnaire completed at the time of enrollment.

Differences in FACT-O scores between patients receiving FWGE and placebo: A paired t-test will be used to test the null hypothesis that there is no difference between baseline PF scores and the PF scores weekly and prior to surgery for those patients randomized to FWGE versus placebo.

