2.2 Objectives

2.21 Primary Pilot Objective: To assess the safety, toxicity and quality of life (QoL) of women with suspected ovarian cancer scheduled to undergo surgery, administered FWGE versus placebo daily for up to 4 weeks.

2.22 Seconday Pilot Objectives:

2.221 To develop pilot data on the impact of FWGE on: the tumor marker CA125, tumor proliferation.

2.222 To develop pilot data on changes in gene expression in ovarian cancer exposed to FWGE versus placebo.

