6.2 Treatment plan

- 6.21 All subjects will undergo:
 - 6.211 history and physical examination within 28 days of study entry.
 - 6.212 laboratory evaluation: complete blood count, differential, comprehensive metabolic panel and CA125 test prior to starting protocol therapy and preoperatively.
 - 6.213 serum pregnancy test (within 7 days of starting study drug), for women of child-bearing potential.
 - 6.214 Evaluation for National Cancer Institute's Common Toxicity Criteria, all grades at the time of enrollment, then weekly and the day of surgery.
 - 6.215 Quality of life questionnaire (FACT-O) at the time of enrollment, then weekly and the day of surgery (Appendix I).
- 6.22 Patients will be randomized to treatment with either FWGE or placebo and assigned a blinded treatment number corresponding to one of the two treatment groups. The pharmacy will label the appropriate blinded drug specifically for the patient. A daily supply of drug will be given to the patient from the study pharmacy. The amount will be determined by the time until the surgical procedure is scheduled. Neither patients nor treating physicians will be informed of patients "treated/control" status.

Participants will undergo their planned surgery within 4th week after entry into the study. However, if there are delays, patients can continue to take drug/placebo

for a time period no greater than 2 months. If surgery has not occurred after this 2-month period, the patient will be removed from the study.

Participants will take the study drug up until the day prior to surgery. A separate consent form will be obtained for the surgical procedure.

6.23 The primary tumor tissue obtained during the subject's surgery will be transferred to the pathology department for processing.

6.231 Formalin Fixation

Tissue will undergo formalin fixation then embedment in paraffin; tumor tissue will be stained using the H&E process and will be examined by light microscopy. The tumor will also be stained by immunohistochemical (IHC) stain for proliferation marker Ki-67 (Anti-Ki67 primary antibody, catalog number 790-2910, Ventana, Tucson, AZ, USA). The proliferation index will be calculated by percent of nuclear staining of the tumor for tumor tissue treated with FWGE versus placebo and the result will be compared. The reading pathologist will be blinded to the treatment group.

6.232 Fresh frozen

An additional specimen, approximately 30mg, will be flash frozen.

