9. EVALUATION CRITERIA

The evaluation criteria for this study are primarily safety, toxicity, and QoL. Secondary assessments are disease response based on CA125, apoptosis and tumor proliferation, 2,6 DMBQ serum levels, and molecular changes as indicated below.

9.1 Safety, Toxicity and Quality of Life: will be assessed as reviewed in section 6.

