12.0 STATISTICAL CONSIDERATIONS

12.1 Study Design: This study is a randomized, double-blind, placebo-controlled, trial of the effect of FWGE on women with epithelial ovarian cancer scheduled to undergo surgery. As noted above, we recognize that the sample size in the current study will prohibit definitive statistical conclusions to be drawn on our primary objective (to test the safety and tolerability of FWGE), or our secondary objectives (to compare levels of FWGE active product, CA125 levels, proliferation, and gene expression in OVCAs from subjects receiving FWGE versus placebo). The study is neither designed nor powered to develop statistically significant results, rather, we seek to develop preliminary/pilot data that will enable us to pursue a future large phase II, peer-reviewed grant-funded

trial of adjuvant FWGE in women undergoing therapy for ovarian cancer. Preliminary data developed in the current proposal will support such grant applications.

- 12.2 Primary outcome variable: The principal parameters to be collected, analyzed and reported will be:
- patient and disease characteristics: age, race, co-morbidities, cancer histologic
 type and stage. Optimal versus suboptimal surgical cytoreduction.
 - differences in toxicity
 - differences in quality of life

For each measure, Student's t-test will be used to identify differences between FWGE-versus placebo-treated OVCAs.

- 12.3 Secondary outcome variables for placebo versus FWGE:
- -the presence of 2,6-dimethoxy-p-benzoquinone in the serum
- -the change in the tumor marker CA125,
- -tumor proliferation as measured by Ki-67.

For each measure, Student's t-test will be used to identify differences between FWGEversus placebo-treated OVCAs.

12.4 Secondary outcome variables for genomic changes in ovarian cancer tissue for placebo versus FWGE.

Expression values will be calculated using the robust multi-array average (RMA) algorithm implemented in the Bioconductor (http://www.bioconductor.org) extensions to the R statistical programming environment.

Student's t-test will be used to identify differentially expressed genes in comparisons between FWGE- versus placebo-treated genomic data. Differentially expressed genes will analyzed using GeneGO MetaCore™ software to identify represented biologic pathways.

12.5 Accrual, Sample Size, and Study Duration: The study plan is a one-stage, randomized, double-blind, clinical trial. Patients will be randomized with equal

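### Section 6.26 names a paired t-test on undefined PF scores for a comparison between arms, and section 12.2 names the right contrast without a score or visit

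*Combined protocol and SAP*

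**What the plan says.** The primary objective in section 2.21 is "To assess the safety, toxicity and quality of life (QoL) of women with suspected ovarian cancer scheduled to undergo surgery", for FWGE against placebo. Section 6.215 sets the data collection: "Quality of life questionnaire (FACT-O) at the time of enrollment, then weekly and the day of surgery".

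Four places bear on the analysis:

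- **Section 6.26, lead-in to the analysis sentence:** "Differences in FACT-O scores between patients receiving FWGE and placebo".
- **Section 6.26, the test:** "A paired t-test will be used to test the null hypothesis that there is no difference between baseline PF scores" and the PF scores taken weekly and before surgery, for women randomized to FWGE versus placebo.
- **Section 12.2:** lists "differences in quality of life" among the principal parameters, then says "For each measure, Student's t-test will be used to identify differences between" the FWGE and placebo groups. It names no FACT-O score or visit, and does not say whether change from baseline is used.
- **Section 9.1:** "Safety, Toxicity and Quality of Life: will be assessed as reviewed in section 6".

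No section says whether the test in 6.26 or the one in 12.2 governs.

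**The concern.** The arms contain different women, so an FWGE-placebo difference needs a two-sample comparison. The paired test in 6.26 compares each woman with her own baseline and answers whether scores moved over time. Scores may move in both arms for shared reasons, such as approaching surgery or disease symptoms. If the movement happens to reach significance in the FWGE arm only, the lead-in invites the reader to call it an FWGE effect.

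The score is also unidentified. PF appears only in that sentence. It could mean physical well-being, functional well-being, or the overall score implied where 6.26 says FACT-O "is a tool that provides a general QoL score". An analyst who turns to 12.2 finds the right contrast but must choose the score and the visit after the data exist.

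At stake is the quality-of-life estimate that this pilot is meant to supply to a later phase II application.

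**Working it through.** **1. The two tests side by side**

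| | Section 6.26 | Section 12.2 |
|---|---|---|
| Stated purpose | FWGE-placebo difference in FACT-O | FWGE-placebo difference in quality of life |
| Test | Paired t, baseline against later | Student's t between arms |
| Quantity tested | Mean change over time | Difference between arm means |
| Score | PF, undefined | None named |
| Visit | Weekly and before surgery, none primary | None named |

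The FACT-O parts listed in 6.26 are physical, social/family, emotional and functional well-being and the Ovarian Cancer subscale: 7 + 7 + 6 + 7 + 12 = 39 items, matching the stated 39. None is called PF there or on the appended form. The same paragraph announces 3 subscales and lists five.

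**2. Inputs for the size of the problem**

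- From section 12.5: 20 women, randomized with equal probability, 18 evaluable (20 × 0.90 = 18). That is about 9 to 10 per arm. The split of the 18 is not stated, so 8/10 is also shown.
- Assumed, because the plan gives none of these: two-sided alpha 0.05, normally distributed change scores, no FWGE effect, and the same drift d in both arms, in SDs of the change score.

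**3. Within-arm significance in the FWGE arm only**

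For n women in an arm, the paired test rejects with probability p(n, d), from the noncentral t distribution with n − 1 df and noncentrality d√n. The arms are independent, so P(FWGE only) = p_FWGE × (1 − p_placebo).

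| Drift d | p, n = 9 | p, n = 10 | FWGE only, 9/9 | FWGE only, 10/10 | FWGE only, 8/10 or 10/8 |
|---|---|---|---|---|---|
| 0 | 0.050 | 0.050 | 0.048 | 0.048 | 0.048 |
| 0.2 | 0.083 | 0.088 | 0.076 | 0.080 | 0.071–0.081 |
| 0.5 | 0.263 | 0.293 | 0.194 | 0.207 | 0.164–0.225 |
| 0.7 | 0.455 | 0.506 | 0.248 | 0.250 | 0.198–0.303 |
| 1.0 | 0.748 | 0.803 | 0.188 | 0.158 | 0.134–0.256 |
| 1.5 | 0.975 | 0.987 | 0.025 | 0.013 | 0.012–0.048 |

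Example, 10 per arm at d = 0.5: 0.293 × (1 − 0.293) = 0.207. With equal arms the probability cannot exceed 0.25. It peaks near d = 0.7 and then falls, because at large drift both arms become significant.

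A two-sample t-test on change removes the shared drift. In simulation (100,000 trials per setting; drifts 0, 0.2, 0.5 and 0.7; splits 9/9, 10/10 and 8/10) it rejected in 4.9% to 5.2% of trials.

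**4. No primary visit**

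With no drift and every post-baseline visit tested at 0.05, let q be the chance of at least one significant paired test in a given arm. For either arm the chance is 1 − (1 − q)². Simulated with 60,000 arms at n = 9 and n = 10:

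| Visits | One arm, equal correlation | One arm, AR(1) 0.7 | Either arm, equal correlation | Either arm, AR(1) 0.7 |
|---|---|---|---|---|
| 2 | 9% | 9% | 17% | 17% |
| 3 | 13% | 12% | 24% | 22% |
| 5 | 19% | 17% | 34–35% | 30–31% |
| 9 | 29% | 24% | 49% | 43% |

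Five visits means four weekly assessments plus the day of surgery under the 4-week plan. Nine means eight weekly plus surgery at the 2-month limit in section 10. That is an extreme case, because it assumes every woman is delayed that long.

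**5. What the two-sample analysis would deliver**

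The 95% CI half-width for the difference in mean change is t(0.975, 2n − 2) × √(2/n), in SDs of the change:

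- 9 per arm: 2.120 × √(2/9) = 1.00 SD
- 10 per arm: 2.101 × √(2/10) = 0.94 SD

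**The case against.** The strongest reply is that the plan already contains the right test. Section 12 is the statistical section and assigns a between-arm t-test to quality of life; 6.26 can then be read as a separate within-arm analysis. Section 9.1 need not promote 6.26 over 12.2 either: for safety and toxicity, section 6 holds an assessment schedule rather than an analysis, so being assessed there may simply mean being measured. PF may be a drafting slip for the FACT-O score.

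This lowers the weight but does not remove the error. On that reading 6.26 still labels a within-arm result as a difference between arms, PF is still undefined, and 12.2 still lacks a score, a visit and a change rule. No reading of the text yields one fully specified between-arm analysis.

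The second reply is that the protocol disclaims statistical significance in sections 2.1, 3.4 and 12.1, and sets no alpha and no decision rule for quality of life. That stands. The rejection rates above illustrate how the two tests differ; they are not operating characteristics the sponsor has claimed. They mislead only if a within-arm p-value is read as an arm difference, the documents support no particular drift, and the visit-level rates assume uncorrected testing at every visit. Because surgery is planned within the fourth week, five post-baseline visits is also nearer an upper bound than a typical count.

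**Conclusion.** The concern holds and should be fixed. For a component of the primary objective, 6.26 states a test that cannot estimate the quantity its lead-in promises, on a score that does not exist under that name. Section 12.2 names the right contrast but leaves it underspecified.

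Under the stated assumptions, reading the 6.26 result as an arm difference would point to an FWGE effect that does not exist in about 19% to 25% of trials at shared drifts of 0.5 to 0.7 SD, and less often at smaller or much larger drifts. The two-sample test keeps the rate at 5%.

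The consequence is a misleading or post hoc pilot estimate, not a failed power claim. The text findings need no assumptions; only the percentages do.

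**What to change.** In 6.26, replace the paired t-test and the PF label with one between-arm analysis, and state the same analysis in 12.2:

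- one named FACT-O score, for example the total;
- one named visit, for example the day of surgery;
- change from baseline compared between arms by two-sample t-test;
- the FWGE-placebo difference reported with its 95% CI.

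Keep weekly and within-arm changes as descriptive summaries, without tests. Correct the subscale count in 6.26 at the same time.

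ANCOVA on the baseline score is an optional alternative. With 18 to 20 women its variance would be about 80% (baseline correlation 0.5) to 91% (0.7) of the change-score analysis, for one degree of freedom; both correlations are assumed.

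The cost is protocol wording only. FACT-O is already collected at baseline, weekly and on the day of surgery (sections 6.215 and 8.1), so no data, visit or sample-size change is needed.

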7. TREATMENT MODIFICATIONS

- 7.1 It is expected that the dose of FWGE used in this study will be well tolerated; therefore there will be no dose modification. Specimens will be collected from all patients who undergo surgery even if they do not complete the full course of medication.
- 7.2 Criteria for removal from study:
 - 7.31 Patient refusal to continue treatment.
 - 7.32 Patient non-adherence to study plan.
 - 7.33 Pregnancy
 - 7.34 Patient does not have surgery within 2 months of starting FWGE or placebo.
 - 7.35 Grade 3 or 4 allergic reaction to FWGE or placebo

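### Women removed under Section 7.2 may drop out of toxicity and quality-of-life follow-up, because the protocol does not separate stopping product from leaving the study

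*Combined protocol and SAP*

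**What the plan says.** - **Primary objective.** Sections 2.21 and 9 make safety, toxicity and quality of life primary.
- **Schedule.** Section 6.21 begins "All subjects will undergo". Item 6.214 then requires grading by "Common Toxicity Criteria, all grades at the time of enrollment, then weekly and the day of surgery", and item 6.215 requires "Quality of life questionnaire (FACT-O) at the time of enrollment, then weekly and the day of surgery". Sections 8 and 8.1 repeat this schedule.
- **Removal.** The heading "7.2 Criteria for removal from study" covers five items, numbered 7.31 to 7.35. Three matter here: "Patient refusal to continue treatment" (7.31), "Patient non-adherence to study plan" (7.32) and "Grade 3 or 4 allergic reaction to FWGE or placebo" (7.35).
- **Incomplete course.** Section 7.1 states: "Specimens will be collected from all patients who undergo surgery even if they do not complete the full course of medication". It has no matching sentence for toxicity grading or FACT-O.
- **FACT-O window.** Section 6.26 limits the questionnaire to time points while the woman is participating in the study.
- **Other status terms.** The unblinding paragraph (the second Section 5.4) uses a separate off-treatment status. Section 6.22 uses study-removal wording for a woman without surgery by 2 months, which Section 10 sets as the longest time on study.
- **Analysis.** Section 12.5 expects 18 evaluable cases from 20 accruals. It does not define evaluable or say how removed women are analysed.

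**The concern.** Refusing further product and having an allergic reaction can both be consequences of poor tolerability, and non-adherence sometimes is. If those events end assessment, the primary endpoints go missing for reasons related to the endpoints themselves, and the women who remain are a selected group.

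The loss need not favour one arm. Taste, disease symptoms or logistics could cause removal in either arm, so neither the direction nor the size of any bias can be stated in advance. With 10 women planned per arm, each is 10% of her group. The pilot is meant to supply safety and quality-of-life data for a phase II proposal, so incomplete follow-up matters even though no significance test is relied on.

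The text also has an imbalance. It provides for collection after an incomplete course for specimens, which serve secondary endpoints (Ki-67, gene expression), but not for the primary data.

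**Working it through.** **Reading the sections together**

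1. Where Section 6.22 speaks of removal at 2 months, Section 10 shows that this means the end of study participation. Section 7.2 uses the same kind of wording.
2. The unblinding paragraph shows that the protocol has a distinct term for being off treatment. Section 7.2 does not use it.
3. Section 6.26 ties FACT-O to participation, which suggests that it stops at removal.
4. Nothing says outright that assessments stop at removal, and nothing says that they continue. Stopping is the natural reading of Section 7.2.

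**The plan's own figure**

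20 × (1 − 0.10) = 18, so the 18 evaluable cases in Section 12.5 reproduce. No alpha, power, effect size or SD is given, so there is no power figure to check.

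**Illustration 1: assessments lost**

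Assumptions: 10 women per arm (Sections 2.1 and 3.4); the same course of W weeks for all; W post-baseline assessments each (weeks 1 to W − 1 and the day of surgery); k women removed just after week 1. Each removed woman misses W − 1 of W, so the share of the arm lost is k(W − 1)/(10W).

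| Course | k = 1 | k = 2 |
|---|---|---|
| W = 2 | 1/20 = 5% | 10% |
| W = 4 | 3/40 = 7.5% | 15% |
| W = 8 (about the 2-month limit) | 7/80 = 8.75% | 17.5% |

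Section 12.5 expects under 10% of patients lost for any reason, so two removals in one arm is a stress case.

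**Illustration 2: FACT-O**

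Assume removed women would have scored d = 0.5 to 1 SD worse than those who stay. The arm mean is then overstated by (k/10) × d:

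- k = 1: 0.05 to 0.10 SD
- k = 2: 0.10 to 0.20 SD

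For the two-sample t-test of Section 12.2, SE = √(1/(10 − k) + 1/10):

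- k = 1: √(1/9 + 1/10) = 0.459 SD
- k = 2: √(1/8 + 1/10) = 0.474 SD
- Shift in SE units: from 0.05/0.459 = 0.11 to 0.20/0.474 = 0.42

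For the within-arm paired t-test of Section 6.26, SE = √(2(1 − ρ)/(10 − k)). The within-woman correlation ρ is not given; assume 0.5 to 0.8:

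- ρ = 0.5: 0.333 SD (k = 1), 0.354 SD (k = 2)
- ρ = 0.8: 0.211 SD (k = 1), 0.224 SD (k = 2)
- Shift in SE units: from 0.05/0.333 = 0.15 to 0.20/0.224 = 0.89

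**Illustration 3: toxicity**

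Assume that events recorded before removal are kept. Only events that first appear or worsen afterwards can then be missed. The most that can be lost is 1/10, or 10 percentage points of the arm's incidence, per removed woman.

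**The case against.** The strongest reply is that the harm is inferred from silence.

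- **The schedule makes no exception.** Sections 6.21, 8 and 8.1 run the assessments to the day of surgery and do not exempt women off product. Section 7 is headed as treatment modification, so leaving treatment may be all that was meant. Section 7.1 expects women with an incomplete course to reach surgery, where the final grading and questionnaire also fall. These points show that continued follow-up may have been intended, but none says that a removed woman stays on the schedule.
- **Safety is partly covered.** Section 11.1 does not limit adverse events to time on study, Section 11.2 requires follow-up of serious events, and the event that triggers removal would normally already be recorded. This stands. It narrows what is at risk to later routine toxicity grades and FACT-O.
- **The shifts are small.** This also stands. The between-arm figure stays under half a standard error. The 0.89 SE in the paired case combines two removals, a 1 SD deficit and ρ = 0.8. With that ρ the SD of change is √0.4 = 0.63 SD, so the deficit is about 1.6 SDs of change, which is extreme. The protocol itself disclaims definitive conclusions.
- **Assessing only while on product is a legitimate choice.** It is, but the plan does not state that choice.
- **The consent pages are not in the reviewed text.** They may address data collection after stopping. That cannot be checked here, and Sections 6 and 7 would still need to agree.
- **Non-adherence may itself mean missed assessments.** A wording change cannot recover those data.

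**Conclusion.** The concern holds and should be fixed. Followed as written, Section 7.2 can end collection of the primary toxicity and quality-of-life data for reasons related to tolerability, and no other section prevents this.

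The number of removals and the size and direction of any bias cannot be determined from the documents. The calculations illustrate scale only and rest on assumed timing, deficit and correlation. For one or two removals in an arm they give a modest loss of data and a shift that is small beside the sampling error of the between-arm comparison. This is therefore a matter of keeping the pilot's primary data complete and interpretable, not a flaw that invalidates the design. Confidence is medium, because the intended meaning of removal is not certain.

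**What to change.** Leave the listed criteria unchanged and reconcile Sections 6.21, 7.1 and 7.2:

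1. Distinguish stopping product from leaving the study.
2. State that CTCAE grading and FACT-O continue on the existing schedule for every randomised woman, to the day of surgery or, without surgery, to the existing 2-month limit, unless she withdraws consent to data collection.
3. Replace the undefined evaluable count in Section 12.5 with named analysis sets: toxicity in all women who took at least one dose, and quality of life in all randomised women with available data.
4. Report removals by arm, with reasons.

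The cost is a small wording amendment and a few more questionnaires and toxicity assessments in women who have stopped product. No new procedure is needed.
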